8.5. Discontinuation of Study Medication

If a subject becomes pregnant during the study, the subject will be withdrawn from study medication and followed through the conclusion of the pregnancy (Section 9.6).

Subjects may be discontinued from study medication because of either of the following:

- Adverse event: A clinically significant or serious AE that in the Investigator's or Medical Monitor's judgment, suggests that continued administration of study medication is not in the subject's best interests for safety reasons. Additionally, if an AE requires treatment, the Investigator in consultation with the Medical Monitor may determine that study medication should not be concurrently administered with a required concomitant medication.
- Subject request: Subject requests to be withdrawn from study medication.

When possible, a decision to discontinue a subject from study medication should first be discussed with the Medical Monitor. If a subject is discontinued from study medication, every effort should be made to encourage the subject to continue to attend study visits to be followed for safety, rather than withdrawing the subject from the study or, failing that, to perform all early discontinuation assessment procedures at the visit the subject is withdrawn (Section 10.3). Reasons for considering subject withdrawal from the study are discussed in Section 7.3.

8.6. Study Medication Materials and Management

8.6.1. Packaging and Labeling

Study medication will be packaged and labeled at a central packaging facility. Study sites will utilize the IWRS to assign kits to subjects.

8.6.2. Storage and Administration

Study medication must be stored at room temperature 15°-25° C (59°-77° F). A room temperature log will be maintained at each study site. Subjects should be instructed not to store or place the study medication where it can be exposed to extreme temperatures (e.g., refrigeration or leaving it in a hot car) or light. The study medication will be provided in a child-resistant package. Importantly, subjects MUST store the eye drops out of reach of children at all times. Accidental ingestion by young children can result in serious adverse events. If a child accidentally swallows these eye drops, call the National Capital Poison Center ([name]) and seek emergency medical care immediately.

Site personnel will instruct the subject on the proper instillation technique at Day 1 (Visit 2) and the subject (or caregiver, if the subject is not able to self-administer the medication) will administer the first dose at the study site, instilling 1 drop in each eye from the unit-dose vial

The subject should be in a seated position and should tilt his or her head backward for administration of the study medication. The vial of study medication should be held at an almost vertical position above the eye while the lower eyelid is pulled down gently, and 1 drop is placed into the conjunctival cul-de-sac. The tip of the vial should not touch the eye. After a drop is instilled in each eye, the subject should keep the eyes gently closed for approximately 30 seconds. The subject will then empty the remaining contents of the unit-dose vial and place the empty vial in the pouch.

Each subsequent morning of dosing, the subject will open a pouch from the box, administer one drop to each eye from a single new unit-dose vial and close the eyes gently for 30 seconds, empty the remaining contents of the unit-dose vial, then store the opened vial in the foil pouch, and place it in the box for return to the study site. On Day 14 ± 3 days (Visit 3), subjects will return all opened and unopened study medication materials, and site personnel will conduct study medication accountability procedures and dispense study medication for the remaining study period. On Day 42 ± 3 days (Visit 4) the box, complete with opened unit-dose vials/pouches and any unopened study medication will be returned to the study site, and final study medication accountability will be conducted. The Day 42 visit will be the last day of study treatment; no further study medication will be dispensed at this visit.

Note: Contact lens wear is permitted during the study. Contact lenses must be removed prior to instillation of study medication and must not be reinserted for at least 15 minutes after study medication instillation. Contact lenses must not be worn during study visits.

8.6.3. Study Medication Accountability

The Investigator or clinical site staff will maintain a full accountability record for the study medication and will be responsible for recording the receipt, dispensing, and return of all supplies of the study medication using the inventories supplied by the Sponsor. Each subject's kit will contain sufficient study medication for the duration of the trial. Final study medication accountability will be conducted at Day 42 ± 3 days (Visit 4); study medication will not be re-dispensed at this visit. The Investigator or clinical site staff will account for all received and returned study medication. The monitor will review dispensing and study medication accountability records during site visits and at the completion of the study and note any discrepancies. All investigational study medication must be stored in a secure facility with access limited to the Investigator and authorized staff.

9. STUDY ASSESSMENTS

Prior to entry into the study or initiation of any study-related procedures, the subject must read, sign, and date the current IRB-approved version of the informed consent form. For minor subjects, the subject's parent or legal guardian must provide permission by signing the ICF on behalf of the subject, and assent from the minor subject should also be obtained following IRB guidelines. If a subject becomes 18 years of age during the study, the subject will need to sign an ICF to continue in the study. A full discussion of informed consent is presented in Section 13.3. Procedures must be performed in the order specified in Table 2.

9.1. Demographic and Background Characteristics

9.1.1. Demographic/Medical History

A complete medical history will be obtained from each subject. Demographic information including date of birth, gender, race, ethnicity, iris color, and date of informed consent will be recorded.

9.1.2. Concomitant Medications History

All concomitant medications (prescription and OTC) taken at Visit 1 (Screening) and for 3 months prior to Visit 1 and throughout the course of the study will be recorded in the Concomitant Medications page of the eCRF. Information regarding the dates of first and last dose, site of dosing (e.g., right eye, left eye, both eyes [OU], systemic), and the reason the concomitant medication is being taken must be recorded in the eCRF. When a concomitant medication has been taken at a stable dose for longer than 6 months, an estimation of the start date is adequate. Standard procedural medications will not be captured in the eCRF but are recorded on a standard procedural medication log provided by Oculos.

9.1.3. Ophthalmic History and Ophthalmic Intervention History

Clinically significant ophthalmic history and ophthalmic intervention history will be documented and will include any previously diagnosed ophthalmic abnormalities and ocular surgeries, including laser procedures.

9.1.4. Urine Pregnancy Test

A urine pregnancy test will be performed for females of childbearing potential only (females who have started their menstrual cycles).

9.2. Efficacy Assessments

The efficacy of RVL-1201 Ophthalmic Solution compared to the Vehicle for the pharmacologic treatment of acquired blepharoptosis will be measured by improvement in visual field (as determined by LPFT assessment) and increase in MRD.

9.2.1. Leicester Peripheral Field Test

The LPFT, a customized visual field test designed specifically to assess ptosis (Ho et al, 2011), will be performed using a Humphrey Visual Field Analyzer. It is an age-corrected screening test with a three-zone strategy. Thirty-five points are tested in the superior field while 14 points are tested in the inferior field. A maximum of 48° is tested in the superior visual field. The center of fixation is shifted 15° inferiorly to allow for maximum superior field testing (Ho et al, 2011). The inferior field test serves as a reference but is not used in the analysis.

[figure not shown]

Figure 1: Leicester Peripheral Field Test Grids

Clinical site staff must instruct the subjects to keep their chin and forehead against the chin and forehead rests, and to keep their brows relaxed. Clinical site staff must also instruct the subjects to look at the fixation target throughout the test. A corrective lens is not necessary on the LPFT UNLESS the subject would have a difficult time seeing the target without it (e.g., high myope, high hyperope, or high astigmat).

There are two types of scores for the LPFT assessment:

LPFT Eligibility Score: The total number of points missed in the top 2 rows on the LPFT.

LPFT Total Score: The total number of points seen in the top 4 rows on the LPFT.

Leicester Peripheral Field Test assessments will be performed OU until the point of study eye designation by the medical monitor. After designation, LPFT assessments will be performed only on the study eye. For subjects with surgical monovision correction where the study eye is the near vision eye, a neutralizing trial lens may be put in the lens holder located in front of the chin rest of the HVF Analyzer.

The HVF Analyzer will determine if the LPFT test is reliable. If the HVF Analyzer issues an "XX" for fixation losses, false positives, and/or false negatives, the test will be deemed unreliable. If deemed unreliable, the test must be retaken (once per scheduled test). If the outcome of the repeated test is reliable it will be used in the efficacy analysis, and if the repeated test is unreliable it will be included in the ITT analysis set but excluded from the PP analysis set.

9.2.2. External Photography

An external photograph of the subject's face will be taken using the provided digital camera. It is crucial that the same level of ambient lighting be maintained for each photograph throughout the study. The subject will be required to remove mascara and any other eyelid makeup if applicable. The subject will also be asked to relax his/her facial muscles. The photograph will frame the subject's face from mid-forehead to the tip of the nose vertically and from ear-to-ear horizontally. A standardized millimeter ruler label will be placed vertically on the forehead, centered above the eyebrows, as a measurement legend. All measurements (MRD and pupil diameter) will be made from the digital image or color printed copy of the photograph using a handheld caliper and the millimeter ruler label as the legend.

9.2.2.1. Marginal Reflex Distance Measurement

The distance from the center pupillary light reflex to the central margin of the upper eyelid is the MRD. The MRD will be measured from the external photograph.

9.3. Safety Assessments

Assessment of the safety and tolerability of RVL-1201 Ophthalmic Solution compared to Vehicle will include bilateral ophthalmic examinations (Snellen VA, pupil diameter measurement, SLE/CFS, intraocular pressure (IOP) tonometry, dilated ophthalmoscopy/fundus exam), measurement of vital signs, and recording of adverse events. Subject rating of study medication tolerability will also be obtained.

9.3.1. Vital Signs

Blood pressure (from the same arm, and with the same cuff size, appropriate for arm circumference, throughout study) and heart rate will be measured after at least 3 minutes rest in the sitting position. Vital signs may be repeated once, after at least 5 minutes rest in the seated position, if they are out of range.

9.3.2. Snellen Visual Acuity Assessment

Corrected or uncorrected Snellen VA measurement will be performed with the Snellen eye chart using the subject's current corrective lens prescription, if applicable, at a distance equivalent to 20 feet (6 meters). If the corrected or uncorrected visual acuity is 20/80 or better, no additional refraction is necessary. If corrected or uncorrected visual acuity is worse than 20/80, then an updated refraction must be performed. This refraction must be used for all VA and visual field (if applicable) assessments during the study. The subject must wear the same glasses (if applicable) at each visit. The updated refraction can be placed in a trial frame or phoropter for VA assessments, and the trial frame only for visual field (if applicable) assessments.

For subjects with surgical monovision correction, VA assessment may be conducted in the near vision eye with a near vision reading card held at approximately 14 inches from the subject's eye.

9.3.3. Pupil Diameter Measurement

Pupil diameter will be measured (either horizontally or vertically if top of pupil is not visible in photograph) from the external photograph (see Section 9.2.2).

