4. INTRODUCTION

RevitaLid Inc. (RevitaLid) is pursuing the development of RVL-1201 Ophthalmic Solution (oxymetazoline hydrochloride ophthalmic solution, 0.1%) for the treatment of acquired blepharoptosis (ptosis). Ptosis is experienced by approximately 12% of adults over the age of 50 (Sridharan et al, 1995). It is a unilateral or bilateral abnormal drooping of the upper eyelid that usually occurs from a partial or complete dysfunction of the muscle(s) that elevate the upper eyelid: the levator palpebrae superioris and/or Müller's muscle. Patients with ptosis may experience significant superior visual field defects, which can affect daily activities such as driving, crossing streets, and reading.

Treatment for acquired ptosis usually involves surgery, with risks of infection, bleeding, over- or undercorrection, reduced vision, and lagophthalmos (inability to close the eyelids completely) (Finsterer, 2003). Mechanical treatment of ptosis (scleral contact lenses with a bar to lift the eyelid (Shah-Desai et al, 2010), eyelid ptosis crutches attached to glasses, or adhesive tape or putty to affix the upper eyelid to the supraorbital structures) is limited by patient dissatisfaction with physical appearance, contact allergies, or skin irritation. Pharmacologic treatment of ptosis has not been pursued because the agents that have been evaluated (e.g., epinephrine, dipivefrin, apraclonidine, phenylephrine, brimonidine) either caused mydriasis, resulting in blurred vision or photophobia, or unacceptable systemic side effects (Matjucha, 2011; Scheinfeld, 2005; Kass et al, 1979; Fraunfelder and Scafidi, 1978).

Oxymetazoline is a direct-acting α_2 -adrenergic agonist that has been used at a 0.025% concentration as an ocular vasoconstrictor for nearly 30 years and at a 0.05% concentration as a nasal decongestant for almost 50 years. When administered at a 0.1% concentration it stimulates the α_2 adrenergic receptors in Müller's muscle causing it to contract, thereby lifting the upper eyelid, and retracting the lower eyelid to a lesser degree. Topical ophthalmic administration of oxymetazoline hydrochloride at lower concentrations (0.01%, 0.025%) results in vasoconstriction and reduction of hyperemia but does not have the pharmacologic effect of raising the upper eyelid.

RVL-1201 Ophthalmic Solution contains oxymetazoline hydrochloride 0.1% as the active ingredient, and it is provided in preservative-free unit-dose vials.

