7. SELECTION AND WITHDRAWAL OF SUBJECTS

7.1. Inclusion Criteria

- 1. Males or females ≥ 9 years of age.
- 2. Presence of all the following at Screening:
 - a. Loss on a reliable LPFT of ≥ 8 points in the top 2 rows (LPFT Eligibility Score); subjects must see at least 9 total points in the top 4 rows (LPFT Total Score).
 - i. These criteria must be met in both the V1H0 and V1H6 LPFT assessments
 - ii. There must be ≤ 4 points of variance between the V1H0 and the V1H6 LPFT Eligibility Score; AND
 - b. The MRD, the distance from the central pupillary light reflex to the central margin of the upper lid, ≤ 2 mm (no visible central pupillary light reflex defaults to 0) in the same eye as Inclusion Criterion #2a; AND
 - c. Snellen VA of 20/80 or better in the same eye as Inclusion Criteria #2a and #2b).
- 3. Presence of all the following at Baseline:
 - a. Loss on a reliable LPFT of ≥ 8 points in the top 2 rows (LPFT Eligibility Score) in the same eye as Inclusion Criterion #2a; subjects must see at least 9 total points in the top 4 rows (LPFT Total Score).
 - i. These criteria must be met in the V2H0 LPFT assessment.
 - ii. There must be ≤ 4 points of variance between the V1H6 and the V2H0 LPFT Eligibility Score; AND
 - b. MRD, the distance from the central pupillary light reflex to the central margin of the upper lid, ≤ 2 mm (no visible central pupillary light reflex defaults to 0) in the same eye as Inclusion Criterion #2a; AND
 - c. Snellen VA of 20/80 or better in the same eye as Inclusion Criteria #2a and #2b).
- 4. Females must be 1-year postmenopausal, surgically sterilized, or females of childbearing potential (females who have started their menstrual cycles) with a negative urine pregnancy test at Visits 1 and 2. Females of childbearing potential must use an acceptable form of contraception throughout the study. Acceptable methods include the use of at least one of the following: intrauterine (intrauterine device), hormonal (oral, injection, patch, implant, ring), barrier with spermicide (condom, diaphragm), or abstinence.
- 5. Must be able to self-administer study medication or to have the study medication administered by a caregiver throughout the study period.

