11.6. Safety Analyses

The safety of RVL-1201 will be compared to Vehicle with analysis of safety variables including bilateral ophthalmic examinations (Snellen VA, SLE/CFS, measurement of pupil diameter from external photographs, dilated ophthalmoscopy/fundus examination, and tonometry), vital signs (BP/HR), and AEs. The ocular tolerability of study medication will be rated by the subject. Safety data will be presented in tables of descriptive statistics and frequency distribution. All summary tables will be supported with individual subject data listings.

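### Section 9.3.3 permits a vertical pupil reading when the lid hides the top of the pupil and fixes no axis over time, so lid lift can appear as pupil dilation

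*Protocol*

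**What the plan says.** Protocol section 9.3.3 is the only place that sets the axis: "Pupil diameter will be measured (either horizontally or vertically if top of pupil is not visible in photograph". It does not ask for the same axis at every visit.

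The surrounding text supplies the context:

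- **Image and tool (section 9.2.2):** "All measurements (MRD and pupil diameter) will be made from the digital image or color printed copy of the photograph using a handheld caliper". MRD and pupil size therefore come from the same kind of image.
- **MRD (section 9.2.2.1):** "The distance from the center pupillary light reflex to the central margin of the upper eyelid is the MRD".
- **Entry (section 7.1):** the qualifying eye must have MRD "≤ 2 mm (no visible central pupillary light reflex defaults to 0) in the same eye as Inclusion Criterion #2a".
- **Drug effect (section 4):** the drug acts on Müller's muscle, "causing it to contract, thereby lifting the upper eyelid".
- **Why pupil size is watched (section 4):** agents tried before "either caused mydriasis, resulting in blurred vision or photophobia" or had unacceptable systemic effects.
- **Use (section 11.6):** the safety variables compared with Vehicle include "measurement of pupil diameter from external photographs". They are presented descriptively.
- **Timing (Table 2 and section 10):** pupil diameter is read in both eyes at Screening, at Hours 0, 2, 6 and 8 on Days 1 and 14, after the dose on Day 42, and at early discontinuation.

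**The concern.** The condition in section 9.3.3 can attach to the vertical option alone or to both options. Either way, a vertical reading is allowed when the lid covers the top of the pupil. In that eye a vertical caliper reading runs from the lid margin to the lower pupil edge, so it depends on lid position as well as pupil size.

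The clause looks inverted, since a hidden upper edge is a natural reason to measure horizontally.

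The resulting error is linked to treatment. Lid lift is the intended effect of RVL-1201, so a reading that grows with lift will tend to grow more in that arm. The same happens if an eye is read vertically at baseline and horizontally once the lid has risen. At stake is a false sign of mydriasis, an effect that the Introduction gives as a problem with earlier agents.

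**Working it through.** The protocol gives no pupil figure to reproduce, so the check is geometric.

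**Inputs**

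- From the protocol: MRD of 2 mm or less at entry; MRD runs from the light reflex to the upper lid margin; a hidden reflex is scored 0.
- Assumed, because the protocol gives no values: round pupil of diameter D (radius r = D/2), light reflex at the pupil centre, D of 3 to 5 mm, lid lift L of 0.5 or 1.0 mm, and baseline MRD m uniform on 0 to 2 mm.

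**Formulas**

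- The top of the pupil is hidden when m < r.
- Vertical reading = r + min(m, r).
- Horizontal reading = D whenever the lid is at or above the pupil centre.
- False change on vertical readings, true pupil constant = min(m + L, r) − min(m, r).

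**How many eyes are exposed.** The top is hidden for m < 1.5 mm when D = 3, for m < 2 mm when D = 4, and in every qualifying eye when D is 5 mm or more.

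**One eye.** D = 4, m = 0.5, L = 1. Before lift the reading is 2 + 0.5 = 2.5 mm; after lift it is 2 + 1.5 = 3.5 mm. That is +1.0 mm with no pupil change.

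**One eye, axis changed.** D = 4, m = 1, L = 1. The vertical reading before is 2 + 1 = 3 mm. After lift the top is visible and the horizontal reading is 4 mm, again +1.0 mm.

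**Average over m uniform on 0 to 2 mm, every eye read vertically**

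| D (mm) | L = 0.5 mm | L = 1.0 mm |
|---|---|---|
| 3 | +0.31 | +0.50 |
| 4 | +0.44 | +0.75 |
| 5 | +0.50 | +0.94 |

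For D = 4 and L = 1, the change is 1 for m from 0 to 1, and 2 − m for m from 1 to 2. The average is (1 + 0.5)/2 = 0.75.

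**Dependence on the share of eyes read vertically.** Take D about 4 mm (SD 0.7) and m uniform on 0 to 2 mm, where 93% of eyes have the top hidden at baseline. The mean false difference from extra lift in the active arm is:

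| Extra lift (mm) | All vertical | Half | None |
|---|---|---|---|
| 0.5 | 0.42 | 0.21 | 0 |
| 1.0 | 0.74 | 0.37 | 0 |

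**Limit of a horizontal reading.** A recorded MRD of 0 includes eyes whose lid lies below the pupil centre. At distance d below centre the widest visible horizontal width is 2√(r² − d²). For D = 4 this is 3.87 mm at d = 0.5 and 3.46 mm at d = 1. Lifting the lid from 1 mm below centre to the centre would then add 4.00 − 3.46 = 0.54 mm horizontally. Vertically, the visible extent r − d would go from 1 to 2 mm, adding 1.0 mm.

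**The case against.** The strongest reply is that section 9.3.3 asks for a pupil diameter and offers the horizontal axis by name. A competent reader facing a covered pupil would measure across it, and the distance from lid to lower pupil edge is not a diameter. On that view the sentence is clumsy drafting with little practical effect. The variable is also descriptive, feeds no test or decision rule, and any error makes the active arm look worse.

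Much of this stands. A reader might infer that the rule orders vertical readings and that false dilation will be recorded. The text does not support that, because it permits a vertical reading without requiring one. The millimetre figures are likewise not a forecast of an arm difference. They are within-eye changes with every eye read vertically, and any lid rise under Vehicle would narrow the contrast. Nor could lift hide true mydriasis: it can only add to a vertical reading, so at most it could offset a true constriction.

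The reply does not rescue the wording. No reading of the sentence rules out the vertical axis in a covered eye, and nothing requires one axis over time. The protocol does fix the arm and cuff for blood pressure, the glasses for acuity, the type of tonometer and the lighting for photographs. Descriptive reporting does not remove a bias that follows treatment.

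**Conclusion.** The point holds as a defect in a measurement rule. Followed literally, section 9.3.3 permits the axis that depends on lid position in the eyes where that matters, and it leaves the axis free to change between time points. Lid lift can then be recorded as dilation, mainly under RVL-1201.

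With every eye read vertically, the false within-eye change is about 0.5 to 0.9 mm for a 1 mm lift and about 0.3 to 0.5 mm for a 0.5 mm lift. It falls in proportion to the share of eyes read vertically, and the protocol gives no figure for that share. These values rest on the assumed pupil sizes, lifts and MRD distribution. They apply to qualifying eyes; a fellow eye with a higher lid would show less or none.

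It would go too far to say that horizontal reading removes the error completely. That is true only with the lid at or above the pupil centre, and the rule "no visible central pupillary light reflex defaults to 0" means that a recorded MRD of 0 does not guarantee it.

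The LPFT primary and MRD secondary endpoints do not use pupil diameter and are unaffected. The matter concerns how far a descriptive safety comparison can be trusted.

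**What to change.** Replace the clause in section 9.3.3 with: Pupil diameter will be measured horizontally at every time point in both eyes. Where the light reflex is hidden (MRD recorded as 0), the widest visible horizontal width will be recorded and flagged as possibly truncated.

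Summarise pupil change with and without the flagged readings. If photographs have already been read, identify the vertical readings and re-read them horizontally from the stored images, masked to treatment, before database lock.

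The cost is one changed passage, a line in the reading instructions, a flag in the case report form and a small amount of re-reading. No new visit or photograph is needed. Some truncation will remain in eyes with the lid below the pupil centre; the flag makes it visible but does not correct it.
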